7.2.5 Treatment discontinuation

The treatment of the patient or study on the subject will be discontinued in case of pregnancy or any disease given in exclusion criteria and in patient with hypersensitivity to drugs. There is no serious adverse effect observed after treatment discontinuation.

8. Assessment Plan: HISTORY RELATED QUESTIONS AND CLINICAL ASSESSMENT

Name:	Age:	Date:	
Addres	ss: Marital status:		Phone No:
•	Menstrual irregularity:		
•	Age of menarche:	_	
•	Hirsutism:		
•	Acne:		
•	Daily physical exercise:		
•	Infertility:		
•	Height (m)		
•	Weight (kg)		
•	BODY MASS INDEX (kg/m2):		_
•	Drug history (current and past me	dications)	:
•	Surgical history:	_	
•	BP:		

_

Pulse: _____

Schedule of assessments

	Screening	Baseline investigations	On treatment	End of treatment	
	14-21 days prior to registration	Within 7 days prior to registration	Within 3 days prior to first dose	After 3 months	
Informed consent					
Clinical assessment (mentioned above) Pelvic ultrasound					
right ovary and left ovary (10 or more follicles. 2 – 9 mm in diameter)					
Other imaging					
FBS RBS					
LH FSH Testosterone					
IL-6 IL-8					
HOME. IR					
Concomitant medications					
Adverse events					
Outcome events					

ASSESSMENT PHASE DEFINITONS AND SPECIAL CIRCUMTANCES

SCREENING

All screening will be done before registration of the patients.

BASELINE

All baseline investigations including (but not limited to) levels of interleukin-6 and interleukin-8, insulin resistance and pelvic ultrasound will be performed before giving treatment to the patient.

ON TREATMENT

Assessment during the treatment will be performed.

END OF TREATMENT

All baseline investigations including (but not limited to) levels of interleukin-6 and interleukin-8, insulin resistance and pelvic ultrasound will be performed 12 weeks after treatment.

FOLLOW UP AFTER TREATMENT

No follow up will be performed.

9. Outcomes and Endpoints:

The outcomes of the study is the change in the levels of interleukin-6 and interleukin-8 with the use of antidiabetic drugs (metformin alone and combination of metformin and pioglitazone). Other symptoms like hirsutism, polycystic ovaries and serum testosterone levels may decrease and menstrual cycles might become become regular.

10. Safety Reporting: PREGNANCY

Follow up in the treatment will be discontinued with pregnancy.

REPORTING OF SERIOUS ADVERSE EVENTS

Any adverse effects that occur during the treatment will be reported.

11. Treatment Information:

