Metformin with the trade name of Glucophage is manufactured by Merck International Pharmaceutical Company Limited. Metformin plus Pioglitazone combination with the trade name of Zolid plus is manufactured by Getz Pharmaceutical Company Limited. We would consistently use these two brands. The dosage will be according to according to body weight.

Cost bearing: The cost of the medicines and investigations will be provided to the study participants by the project managers ([name] and [name])

12. Data Analysis Procedure:

Mean ± SD will be used for numeric data generated from our work. In each arm the mean difference in the interleukin-6 and interleukin-8 values will be calculated using paired sample t test. For between arms analysis, mean difference in the interleukin-6 and interleukin-8 values will be calculated using independent sample t test. Non-parametric statistics will be used if the data is skewed. A cut-off will be calculated for interleukin-6 and interleukin-8 separately using ROC curve analysis. Based on the cut-off, a binary logistic regression analysis will be performed to evaluate the predictive significance of the two treatment arms in reducing the levels of inflammatory markers interleukin-6 and interleukin-8. P-value of < 0.05 will be considered significant. Results will be presented in form of tables & figures. SPSS version 21 will be used for all the statistical analysis.

13. Study committees:

The study will be managed with the help of Graduate Study Committee, Clinical Trial Unit and ORIC of Khyber Medical University, Peshawar, Pakistan.

14. Administrative aspects:

The administrative aspects will be managed with the help of Office of Research, Innovation and Commercialisation (ORIC) of Khyber Medical University, Peshawar, Pakistan.

15. References:

3. Sangeeta S. Metformin and pioglitazone in polycystic ovarian syndrome: a comparative study. The Journal of Obstetrics and Gynecology of India. 2012;62(5):551-6.

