EFFECTS OF METFORMIN AND COMBINATION OF METFORMIN AND PIOGLITAZONE ON PLASMA IL-6 AND IL-8 LEVELS IN POLYCYSTIC OVARIAN SYNDROME

Clinical trial registration number: NCT03117517

Date: 15/03/2018

Statistical analysis:

The normality of the data was tested using Kolmogorov-Smirinov and Shapiro-Wilk tests and histograms. FSH, LH, Prolactin, testosterone, IL-6 and IL-8 were not normally distributed and were log transformed for analysis. In the final results log transformed values were back transformed and presented as geometric means and confidence intervals. Patient demographic data were evaluated at baseline as descriptive statistics and presented as mean \pm SD. Wilcoxon signed rank test was used to analyze and compare number of follicles in right and left ovary in the two groups, and also between baseline and follow-up. Results were presented as Median (interquartile range). The baseline data of anthropometric, hormonal and inflammatory markers were compared between the two groups by independent sample t test. Comparison between baseline and after intervention (of 12 weeks) data was done by paired sample t-test for both groups independently. Post intervention comparison between the two groups was also done by independent sample t-test. The change taking place between baseline and after 12 weeks due to intervention was calculated as difference or Δ . Δ was calculated as value at 12 weeks – value at baseline for hormonal, inflammatory and ovarian size variables. The Δ between the two groups was compared by independent sample t-test. P < 0.05 was considered statistically significant. All analyses were performed using SPSS software, version 21 "SPSS (IBM, Armonk, NY, USA).

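### Follicle number has no per-woman value and no valid between-arm test: right and left ovary are named separately, under a test meant for paired data

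*SAP*

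**What the plan says.** The SAP (Statistical analysis) gives follicle number one sentence on testing: "Wilcoxon signed rank test was used to analyze and compare number of follicles in right and left ovary in the two groups". The same sentence applies the test to change over time as well. Results are to be shown as median and interquartile range. No total or mean over the two ovaries is defined.

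The next sentences define the change Δ as the 12-week value minus the "value at baseline for hormonal, inflammatory and ovarian size variables", and compare Δ between arms by independent-sample t-test. Follicle number is not named there.

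The significance rule is "P < 0.05 was considered statistically significant", and the Protocol (section 12, Data Analysis Procedure) has the same: "P-value of < 0.05 will be considered significant". Neither document mentions an adjustment for multiple tests.

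The Protocol's schedule of assessments (section 8) lists the pelvic ultrasound by side, "right ovary and left ovary (10 or more follicles", so both counts should be available for each woman. Section 9 gives the outcome: "The outcomes of the study is the change in the levels of interleukin-6 and interleukin-8". It mentions polycystic ovaries only as something that may improve.

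**The concern.** The arms differ in a treatment that acts on the whole woman. The Protocol's operational definitions describe metformin as oral, and nothing is directed at one ovary. The woman is randomised, and no objective or hypothesis distinguishes right from left. Two per-side results therefore answer the same question twice, and a finding that one side improved and the other did not would have no interpretation.

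The same sentence has two further gaps. A signed rank test needs natural pairs. Baseline and follow-up in one woman form a pair; a woman on metformin and a different woman on the combination do not. And because follicle number is not in the Δ list, nothing else in the SAP supplies a between-arm comparison of its change. At stake is whether the ultrasound result can be read as a treatment comparison at all and, less importantly, some precision and control of false positives.

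**Working it through.** **The text.** The follicle sentence can be read in two ways.
- Each side's count is compared between arms and over time. The over-time part suits a signed rank test; the between-arm part does not, because its result would depend on how women in one arm happened to be lined up with women in the other.
- Right is compared with left within each arm. The test then fits, but the contrast answers no stated question, and follicle number has no between-arm comparison.

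On either reading the SAP gives no valid between-arm test of follicle change.

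**Inputs.** From the documents: 51 women per arm (Protocol section 5d) and a 0.05 level (both documents; two-sided assumed). Assumed, because the documents give no figure: between-ovary correlation r, a 0.4 SD difference in a single ovary, and equal variance and equal effect on both sides.

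**The plan's own figure.** The 102 women reproduce with 15% and 40% entered as proportions: (1.960 + 0.842)² × 0.275 × 0.725 × 2 / 0.25² = 50.08, so 51 per arm. That calculation concerns IL-6 and IL-8. No figure in the plan was derived for follicle number.

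**False positives.** For two tests at 0.05, the chance that at least one is significant under no effect is 1 − P(|Z₁| < 1.96 and |Z₂| < 1.96), with correlation r. At r = 0 it is 1 − 0.95² = 9.75%; at r = 0.8, 7.8%; at r = 1, 5%.

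**Information.** The mean of two ovaries has (1 + r)/2 times the variance of one, so one ovary carries that fraction of the information in the mean: 50% at r = 0 and 100% at r = 1.

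**Power at equal error.**
- Per-woman mean: the standardised effect is 0.4/√((1 + r)/2) = 0.496, 0.462 and 0.434 at r = 0.3, 0.5 and 0.7. A t-test with 51 per arm then has 69.9%, 63.7% and 58.3% power.
- Separate sides: each Z has mean 0.4 × √(51/2) = 2.02. Critical values that hold the either-side error at 5% are 2.23, 2.21 and 2.18. Power is the chance that at least one |Z| exceeds them (normal approximation).

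| r (assumed) | Either-side false positive, unadjusted | Information in one ovary relative to the mean | Power, separate sides, error held at 5% | Power, per-woman mean | Gain (points) |
|---|---|---|---|---|---|
| 0.3 | 9.5% | 65% | 61% | 70% | about 9 |
| 0.5 | 9.1% | 75% | 59% | 64% | about 5 |
| 0.7 | 8.3% | 85% | 56% | 58% | about 2 |

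These are t and normal approximations. The SAP uses a rank method for follicle counts, so they indicate size rather than exact values.

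**The case against.** The strongest reply is that little turns on this. Follicle number is not a primary or secondary objective, the sample size does not rest on it, and reporting by side follows how the ultrasound is recorded. That stands, and it sets the weight of the point.

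Separate per-side tests are also not stated outright, and a right-versus-left comparison is possible. That stands too, but it does not rescue the plan, because it leaves no treatment comparison. One could also count follicle number under the ovarian size variables in the Δ list. The wording does not say so, and the SAP handles follicle counts by a different method.

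Some stronger readings are tempting but not supported:
- *Testing each ovary halves the information.* This holds only at r = 0. A systemic treatment gives reason to expect positive correlation, and at r = 0.3 to 0.7 one ovary keeps 65% to 85%.
- *The plan suffers both the full error inflation and the full power loss.* These assume different decision rules. A single pre-chosen side has 51.6% power at 0.4 SD but no inflation. If either side counts without adjustment, power is roughly 72%, 68% and 64%, above that of the mean, and the cost is the 8-10% error. If both sides must be significant, the error is below 2%. Only a comparison at equal error is fair.
- *The plural in the Δ list shows that ovarian size is analysed by side.* The plural noun covers hormonal and inflammatory variables as well, so it shows nothing about sides.

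**Conclusion.** The point holds as a minor one. As written, the SAP gives follicle number no per-woman value, no test suited to two independent arms and no named place among the change variables. This rests on the text alone.

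The cost of separate testing depends on assumptions. If either side counts, the false-positive chance is about 8-10% for r between 0.3 and 0.7, and falls to 5% only at r = 1. At equal error, the per-woman mean gains about 9, 5 or 2 points of power at r = 0.3, 0.5 or 0.7, given a 0.4 SD single-ovary effect, equal variance and effect on both sides, and 51 per arm. A reader might infer a serious loss of information or a threat to the trial's main result. The documents support neither: the loss is modest, and the IL-6 and IL-8 conclusions do not depend on follicle number.

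**What to change.** In the SAP:
- Define one follicle number per woman, the mean of both ovaries.
- Compare its 12-week change between arms once, with a rank-sum test or a baseline-adjusted model.
- Keep the signed rank test for change within each arm.
- Add follicle number to the Δ list, naming its own between-arm method.
- Give right and left values descriptively, without tests.

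The cost is one derived variable and no new data. A rule is needed for a woman with an ovary not seen at one visit: use the same ovary or ovaries at both visits, so that her change does not mix different quantities. The SAP is written in the past tense and already reports the distribution of the data, so if results exist the change is a re-analysis and should be labelled as such.

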We designed this study to elucidate the role of metformin and combination of metformin and pioglitazone in reducing the levels of interleukin-6 and interleukin-8 in patients with PCOS. This will help us in deciding a better treatment regimen for patients with PCOS. Interleukin-6 and interleukin-8 may emerge as predictive biomarkers of treatment response.

2. Aims and objectives

OBJECTIVES:

The objectives of this study are

1. Primary

To investigate the changes in the levels of interleukin-6 and interleukin-8 after 3 months treatment with metformin alone and combination of metformin and pioglitazone in patients with PCOS.

2. Secondary

To evaluate insulin resistance in all the groups at baseline and after 3 months of treatment.

3. Hypothesis:

Combination of metformin and pioglitazone may decrease the levels of IL-6 and IL-8 in women with PCOS better than metformin.

4. Operational Definitions:

POLYCYSTIC OVARIAN SYNDROME: Polycystic ovarian syndrome, or PCOS, is a condition characterized by chronic oligo-anovulation, polycytic ovaries and hyperandrogenism.

METFORMIN: An oral hypoglycemic drug that decreases glucose production by the liver

and increases peripheral glucose uptake, used to treat type 2 diabetes.

PIOGLITAZONE: is a thiazolidinedione (TZD) with hypoglycemic (antihyperglycemic, antidiabetic) action to treat diabetes.

INTERLEUKIN-6 is a cytokine that acts as both a pro-inflammatory cytokine and an antiinflammatory myokine. It is in humans encoded by the IL6 gene (5).

INTERLEUKIN-8: is a chemokine produced by macrophages and other cell types such as epithelial cells, airway smooth muscle cells (6) and endothelial cells.

5. Materials and Methods:

a. STUDY DESIGN: Two-Arm Randomized Clinical trial.

b. STUDY SETTING: OPD patients in Mardan Medical Complex, Khyber Medical University

c. STUDY DURATION: Six Months after approval of proposal

d. SAMPLE SIZE:

The sample size was calculated using OpenEpi software. With an expected reduction in interleukin-6 and interleukin-8 values of 15% in the Metformin arm, we would need 102 women with PCOS to demonstrate a 40% reduction in interleukin-6 and interleukin-8 in the Metformin and Pioglitazone arm with a power of at least 80% and a ratio of 1 in the two arms.

Arm#1: 51 women with PCOS will be selected based on the inclusion and exclusion criteria. They will receive metformin according to the body weight with maximum dose of 1000 mg (BD) daily.

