6.1 Target population

Women with PCOS visiting the outpatient department of participating hospitals.

6.2 SAMPLE SELECTION:

Inclusion criteria:

PCOS women will have the following inclusion criteria: age group 20 - 40 years, oligoanovulation, hirsutism, elevated serum testosterone levels, menstrual cycle irregulary. Diagnosis of PCOS on ultrasound will be made on the basis of European Society of Human Reproducion and Embryo/ American Society of Reproductive Medicine (ESHRE/ASRM criteria, 2003) according to which 10 or more follicular cysts ranging in size from 2-9 mm or increased ovarian volume of 10 cm in maximal diameter.

Exclusion criteria:

Women with previous history of cushing syndrome, hyperprolactinemia, late onset congenital adrenal hyperplasia, androgen-producing tumors, pregnancy or those taking medications that alters the biochemical or hormonal profile will be excluded by clinical and medical examination.

6.3 Screening:

Before the study-specific screening and investigations, patient will sign a written informed consent and the investigator will also sign the consent with date.

6.4 Registration:

Subjects will be registered before starting study treatment and a registration number will be allotted. Requests for registration will only be accepted from authorized investigators at sites that have received ethical approval. Treatment would be planned to start after registration. Registration would be done according to the instructions in the protocol only after all screening assessments have been performed and the responsible investigator has both verified the subject's eligibility and signed the completed registration form.

[figure not shown]
Once the registration process has completed as per the instructions in the protocol, the subject will be assigned a subject, study number, and written confirmation of registration will be provided to the site. Individuals must be registered once in this trial.

6.5 Randomization:

Randomization will be performed using Block Randomization technique using online software Sealed Envelope.

Appendix 1

Study Schema

7. Data Collection Procedure:

7.1 PATIENT RECUIREMENT:

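### Within-arm changes in IL-6 and IL-8 cannot be attributed to either regimen, because both arms receive metformin and there is no untreated arm; the between-arm difference in change should be named as primary

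*SAP*

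**What the plan says.** **Design.** Protocol section 5a describes a "Two-Arm Randomized Clinical trial". Sections 5d and 7.1 give metformin to 51 women, and metformin plus pioglitazone to 51. No placebo arm, untreated arm or run-in is described.

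**Aim.** The introduction says the study is to "elucidate the role of metformin and combination of metformin and pioglitazone in reducing the levels of interleukin-6 and interleukin-8 in patients with PCOS". The primary objective (section 2) is "To investigate the changes in the levels of interleukin-6 and interleukin-8 after 3 months treatment with metformin alone and combination of metformin and pioglitazone". The hypothesis (section 3) is comparative: "Combination of metformin and pioglitazone may decrease the levels of IL-6 and IL-8 in women with PCOS better than metformin".

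**Analysis.** Protocol section 12 begins with the within-arm test: "In each arm the mean difference in the interleukin-6 and interleukin-8 values will be calculated using paired sample t test". An independent-samples t-test between arms follows. The SAP also runs paired tests in each group separately. It then defines the change Δ with the sentence "The change taking place between baseline and after 12 weeks due to intervention was calculated as difference" and compares Δ between groups by an independent t-test. Every test uses P < 0.05. Neither document says which analysis is primary or labels the paired tests as descriptive.

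**Entry.** Section 6.2 lists "elevated serum testosterone levels" among the inclusion criteria. IL-6 and IL-8 are not entry criteria.

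**The concern.** The SAP's definition of Δ treats a before-after difference as an effect of the drug. Without an untreated group that difference has other possible sources, and the protocol supplies some of them:

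- Its introduction reports that IL-6 and IL-8 fell in women with PCOS who reduced body weight and insulin resistance, which could follow from enrolment and counselling alone.
- Sections 7.2.1 and 7.2.3 permit NSAIDs and antibiotics and prohibit nothing. Section 7.2 says concomitant drugs are not recorded, although the schedule of assessments has a row for them.
- Assay drift between the two sampling times and the natural course of the condition add to these.

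The paired test cannot separate any of this from a drug effect. A significant result could be reported as metformin, or the combination, lowering IL-6 or IL-8 when no drug effect was needed to produce it.

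The objective and the hypothesis also point to different analyses. The first asks for change within each regimen, the second for a difference between regimens. With no primary analysis named, either could become the headline result.

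**Working it through.** **1. What the trial was sized for.** Reading 15% and 40% in section 5d as proportions of women, with two-sided alpha 0.05, 80% power and a 1:1 ratio, the pooled-variance formula gives

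n = (1.960 + 0.842)² × 2 × 0.275 × 0.725 / 0.25² = 50.1, so 51 per arm and 102 in total.

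This reproduces the plan's figure. The text calls the percentages reductions in values, so the reading as proportions is ours. On either reading the calculation contrasts two arms; it is not a calculation for a paired test.

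**2. What each contrast identifies.** Let T be the average non-drug shift over 12 weeks, M the effect of metformin, and P the added effect of pioglitazone on top of metformin.

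- Change in the metformin arm: T + M
- Change in the combination arm: T + M + P
- Difference in change: P, provided T is the same in both arms

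Neither M nor M + P can be separated from T.

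**3. How often the paired test is significant with no drug effect.** From the documents: n = 51 per arm, P < 0.05, and log transformation of IL-6 and IL-8. Assumed, because the documents give no values: log SD s from 0.4 to 0.8, correlation r between visits from 0.5 to 0.7, a two-sided test, and common non-drug falls f of 5%, 10% and 15%.

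The log shift is −ln(1 − f). The SD of the change is s√(2(1 − r)), from 0.4√0.6 = 0.31 to 0.8√1.0 = 0.80. The noncentrality is (shift / SD of change) × √51, and the critical t on 50 degrees of freedom is 2.009.

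| Fall | Log shift | Shift / SD of change | Noncentrality | Significant falls |
|---|---|---|---|---|
| 5% | 0.051 | 0.06 to 0.17 | 0.46 to 1.18 | 7% to 21% |
| 10% | 0.105 | 0.13 to 0.34 | 0.94 to 2.43 | 15% to 66% |
| 15% | 0.163 | 0.20 to 0.53 | 1.45 to 3.75 | 30% to 96% |

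With no shift, the rate of significant falls would be 2.5%.

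**4. The between-arm test under the same conditions.** A simulation of 20,000 trials with no drug effect gave both arms the same shift, in units of the SD of change. Rejection rates count both directions.

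| Shift | Paired test, one arm | Between-arm test on Δ |
|---|---|---|
| 0 | 5% | 5% |
| 0.2 | 29% | 5% |
| 0.4 | 80% | 5% |
| 0.5 | 94% | 5% |

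**5. Testosterone, a secondary matter.** Suppose the qualifying value is also the baseline, values are normal on the analysis scale, and the cut-off is the median of women screened. All three are assumptions. The expected fall with no drug effect is (1 − r) × 0.798 population SD: 0.4 × 0.798 = 0.32 at r = 0.6, and 0.2 × 0.798 = 0.16 at r = 0.8. Divided by the SD of the change (0.836 and 0.612), these are 0.38 and 0.26, significant in about 76% and 45% of arms. With the cut-off at the 30th to 70th percentile and r from 0.9 to 0.6, the range is about 12% to 97%.

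**The case against.** **The primary objective makes no causal claim.** A reader might infer that the design cannot answer its primary objective. The documents do not support that. The objective asks for changes after three months of treatment, which is temporal wording, and a before-after comparison can describe them. The causal language is in the SAP's definition of Δ and in the purpose statement of the introduction. What remains is the mismatch between objective and hypothesis.

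**The causal words are not attached to the paired test.** They stand in the sentence that defines Δ, and the only test the SAP applies to Δ is between arms. This is fair as to wording. But the mean of Δ within an arm is the quantity a paired test on the same scale examines, and nothing marks those tests as descriptive.

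**The valid comparison is already planned.** The between-arm test is in both documents, it matches the hypothesis, and the SAP already promises geometric means with confidence intervals. All of this stands, and it limits the point to labelling and interpretation.

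**Testosterone is ancillary.** It appears in neither the primary nor the secondary objective. A reader might also infer that selecting women on high testosterone undermines the IL-6 and IL-8 results. It does not do so directly: selection reaches those markers only through a correlation the documents do not give. Even for testosterone, regression to the mean depends mainly on whether the qualifying sample is also the baseline. Section 8 separates screening from baseline investigations, but the text available to us does not settle which visit supplies the testosterone value.

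**The assumed shifts may be too large.** Nothing in the documents supports a non-drug fall of 10% or 15%, and 15% equals the whole reduction expected with metformin. That is why 5% is shown as well; its effect is much smaller.

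**Conclusion.** The point holds as one of attribution and labelling. With metformin in both arms and no untreated group, a within-arm change in IL-6 or IL-8 cannot be credited to metformin or to the combination, and the SAP's causal wording should go. This follows from the design and needs no numerical assumption.

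The size does rest on assumptions. With no drug effect, a significant paired fall would appear in about 7–21% of trials for a 5% non-drug shift, and in 30–96% for a 15% shift, over the assumed SDs and correlations. These figures show what could happen; they do not estimate what did.

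The comparative hypothesis remains answerable, because a shift common to both arms cancels in the between-arm difference. Regression to the mean is a conditional caution for the within-arm testosterone change only.

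**What to change.** - **SAP:** delete the words *due to intervention* from the definition of Δ.
- **Protocol sections 2 and 12, and the SAP:** name the between-arm difference in 12-week change in IL-6 and IL-8 as the primary analysis, in line with section 3.
- **Within-arm changes:** report them as geometric mean ratios with confidence intervals, labelled descriptive, and make no efficacy claim from a paired P value.
- **Testosterone:** where both samples exist, use a baseline draw separate from the qualifying one, and say which was used.
- **Timing:** the SAP is dated 15/03/2018, is written in the past tense and reports which variables were not normally distributed. Date the change and state whether it was made after data were seen.

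The cost is wording, with no new patients or visits. The downside is that the trial gives up any claim that metformin alone lowers IL-6 or IL-8. If the change came after data were seen, naming a primary analysis carries less weight than if it had been prespecified, and the report should say so.

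### The SAP does not carry over the protocol's outcome ranking: hormones and ovarian size are tested between arms under the same P < 0.05 rule as IL-6 and IL-8, with no exploratory label

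*SAP*

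**What the plan says.** Protocol section 2 (Aims and objectives) names the change in IL-6 and IL-8 after 3 months as primary. The only secondary objective is insulin resistance: "To evaluate insulin resistance in all the groups at baseline and after 3 months of treatment". Section 9 (Outcomes and Endpoints) again gives the change in IL-6 and IL-8 as the outcome, then adds "Other symptoms like hirsutism, polycystic ovaries and serum testosterone levels may decrease and menstrual cycles might become become regular", with no rank or test attached. Section 12 (Data Analysis Procedure) plans tests for IL-6 and IL-8 only, with "P-value of < 0.05 will be considered significant".

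The SAP (Statistical analysis) covers more variables. It names FSH, LH, prolactin and testosterone alongside IL-6 and IL-8 as log-transformed variables. It then defines change for all of them together: "Δ was calculated as value at 12 weeks – value at baseline for hormonal, inflammatory and ovarian size variables". The test and the threshold follow at once: "The Δ between the two groups was compared by independent sample t-test. P < 0.05 was considered statistically significant". A separate sentence provides an independent t-test of post-intervention values between the groups and does not restrict it to particular variables. Follicle counts in each ovary are also compared. The SAP identifies no primary endpoint, labels nothing exploratory and makes no multiplicity adjustment. It does not mention HOMA-IR by name.

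**The concern.** Someone working from the SAP alone cannot tell that a testosterone or ovarian-size result ranks below an IL-6 result. Both get the same between-arm tests and the same threshold for being called significant. Suppose IL-6 and IL-8 showed no difference between arms. The SAP would still allow a hormone or ovarian-size difference at P < 0.05 to be reported as statistically significant. Because several such variables are tested, possibly twice each, the chance that at least one crosses the threshold by luck exceeds the 5% that applies to any single test.

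The point concerns only the variables outside the objectives. It does not touch the choice of deciding test for IL-6 and IL-8, or the sample size.

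**Working it through.** **Inputs from the documents.** The threshold is 0.05 per test (SAP; Protocol section 12). The arms have 51 women each (Protocol section 5d). Four hormones are named (SAP). The plan gives no family-wise error rate, so there is no figure of its own to reproduce beyond the 5% per test.

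**Assumptions.**
- Tests are two-sided, since sidedness is not stated.
- Ovarian size counts as one variable, which gives k = 5.
- There is no true arm difference in any of the five.
- The correlation between variables is unknown and is varied from 0 to 0.8.
- The correlation between baseline and 12 weeks is 0.5.

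**Step 1: Δ tests, independent variables.** The chance of at least one P < 0.05 is 1 − 0.95^k. For k = 5, 1 − 0.95^5 = 22.6%. Counting only the favourable direction, 1 − 0.975^5 = 11.9%.

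**Step 2: adding the 12-week tests.** With equal variances and baseline to follow-up correlation r, the Δ and 12-week test statistics for one variable correlate at √((1 − r)/2). At r = 0.5 this is √0.25 = 0.5. The second test is therefore partly new, and each variable has two chances of crossing the threshold. Full independence of all ten tests would give a ceiling of 1 − 0.95^10 = 40.1%.

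**Step 3: simulation with correlated variables, k = 5.**

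| Between-variable correlation | Δ only, either direction | Δ only, favourable | Δ or 12-week, either direction |
|---|---|---|---|
| 0 | 22.6% | 11.9% | 37.9% |
| 0.3 | 20.8% | 10.5% | 35.2% |
| 0.5 | 18.2% | 9.1% | 30.9% |
| 0.8 | 13.0% | about 6.5% | 22.5% |

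The first three rows use 200,000 draws of the test statistics. The last row uses 20,000 simulated trials with actual t-tests at 51 per arm, and its favourable figure is half of 13.0%. The same t-test simulation at correlation 0.5 gives 18.6% and 31.6%, in agreement with the table. Changing r to 0.3 or 0.7 moves results by about 1-2 points.

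**Step 4: sensitivity to the count.**
- The four named hormones alone, on Δ: 1 − 0.95^4 = 18.5% if independent, 15.3% at correlation 0.5 and 11.2% at 0.8.
- Right and left ovary as separate variables (k = 6), on Δ: 1 − 0.95^6 = 26.5% if independent and 20.9% at 0.5.

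Follicle counts are left out of these figures. Counting them would raise the figures.

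**The case against.** The strongest reply is that the trial does have a hierarchy. Protocol section 2 labels the primary and secondary objectives, section 9 names IL-6 and IL-8 as the outcome, and the SAP's title names only those two. Leaving lower-ranked outcomes unadjusted is common in a small trial, and the SAP never claims a 5% family-wise rate. This stands in part: a reader might infer that the trial has no ranking at all, and the protocol contradicts that. What remains is that the SAP, which sets the tests and the significance rule, does not carry the ranking over. Nor does the point require a multiplicity adjustment; a label would do.

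A second reply is that most of the five variables have no direction of benefit in the documents. Section 9 expects improvement in testosterone and polycystic ovaries but says nothing of FSH, LH or prolactin. For testosterone and ovarian size alone, if independent, 1 − 0.95^2 = 9.75% in either direction and 1 − 0.975^2 = 4.9% in the favourable direction. This is fair as to claims of benefit. The SAP's rule, however, lets a difference in any of the five be called significant, whichever way it points.

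Third, the protocol's remark about deciding on a better regimen follows directly from reducing IL-6 and IL-8. The documents do not make hormones or ovarian size a basis for choosing treatment. That also stands: the risk lies in what the significance rule permits, not in a declared intention.

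**Conclusion.** The point holds as a gap in the SAP's labelling that raises the error rate for outcomes outside the objectives. For five variables with no true difference, the chance of at least one P < 0.05 on Δ is about 18% at correlation 0.5 (13-23% over correlations from 0.8 down to 0). With the 12-week tests it is about 31% (23-38%). These figures rest on two-sided tests, the count of five and the assumed correlations. If the SAP's hormonal variables include insulin, that part belongs to the secondary objective and is outside this count.

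Two stronger readings are not supported. One is that a chance significant benefit is likely: on Δ, the favourable-direction figure is only about 7-12%. The other is that the SAP's baseline comparisons ("The baseline data of anthropometric, hormonal and inflammatory markers were compared between the two groups by independent sample t test") add to the risk of a false treatment claim. Those tests precede treatment and cannot show a treatment benefit, and the sentence does not list ovarian size.

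The primary analysis and the sample size are unaffected. This is a cheap improvement to what the trial may conclude from its other variables.

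**What to change.** Add to the SAP:

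- FSH, LH, prolactin, testosterone, ovarian size, follicle counts and anthropometric measures are exploratory.
- Each continuous variable gets one between-arm estimate with a 95% confidence interval. Follicle counts get one between-arm comparison with a suitable interval.
- P values for these variables are nominal. No such result is called statistically significant or used as evidence that one regimen is better.
- The P < 0.05 significance wording applies only to the outcomes the protocol ranks: IL-6 and IL-8, and insulin resistance.

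The SAP is written in the past tense and already reports which variables were not normally distributed. If the labels are added after data were seen, the SAP and the report should say so.

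The cost is a few sentences, with no new data or patients. The downside is that a hormone, ovarian-size or follicle difference can be reported only as hypothesis-generating.
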